3. ABBREVIATIONS

The following abbreviations and specialist terms are used in this study protocol.

Table 2: Abbreviations and Definition of Terms

Abbreviation/Specialist Term	Definition
AE	adverse event
ANOVA	analysis of variance
AUC	area under the concentration versus time curve
AUC _∞	area under the concentration versus time curve from time 0 extrapolated to infinity
AUC _t	area under the concentration versus time curve from time 0 to the last measurable concentration (time t)
BGM	blood glucose measurement
BMI	body mass index
C _{max}	maximum observed concentration
CRF	Case Report Form
CRO	Contract Research Organization
CTCAE	Common Terminology Criteria for Adverse Events
CV%	coefficient of variation expressed as a percentage
DBP	diastolic blood pressure
DNA	deoxyribonucleic acid
ECG	electrocardiogram
eCRF	electronic Case Report Form
EDC	electronic data capture
FDA	United States Food and Drug Administration
GCP	Good Clinical Practice
GLP	Good Laboratory Practice
GMP	Good Manufacturing Practice
HR	Heart Rate
ICF	Informed Consent Form
ICH	International Council for Harmonization
IEC	Independent Ethics Committee
IM	intramuscular(ly)
IMP	investigational medicinal product
ITT	Intent-to-treat
LDL	low-density lipoprotein
LOQ	limit of quantification
LPLV	last patient last visit
MedDRA	Medical Dictionary for Regulatory Activities
MTD	maximum tolerated dose
NOAEL	no observed adverse effect level
OECD	Organization for Economic Cooperation and Development
OHRP	Office for Human Research Protections
QTc	corrected QT interval

Abbreviation/Specialist Term	Definition
QTcF	QT interval corrected for heart rate using Fridericia's method
RBC	red blood cell
REB	Research Ethics Board
SAE	serious adverse event
SAP	Statistical Analysis Plan
SBP	systolic blood pressure
SC	subcutaneous(ly)
SD	standard deviation
SOP	standard operating procedure
SUSAR	Suspected Unexpected Serious Adverse Reaction
$t_{1/2}$	elimination half-life
TEAE	treatment-emergent adverse event
t_{max}	time to maximum observed plasma concentration
UP	Unanticipated Problems
WBC	white blood cell
WHO	World Health Organization
YSI	Yellow Springs Instrument

4. INTRODUCTION

4.1. Study Rationale

Exercise is at the cornerstone of Type 1 diabetes (T1D) management [1]. However, blood glucose stability during exercise, and for 12-24 hours afterwards, remains a major challenge [2]. Fear of hypoglycemia deters many patients from engaging in aerobic exercise [3]. For those who choose to exercise on a regular basis, hypoglycemia is a common complaint that often requires breaks in exercise sessions, sports and competition, games and training [3]. To reduce the incidence of hypoglycemia during and immediately after exercise, patients are recommended to reduce their bolus dose at the meal preceding exercise by 25-75% [4], however, this approach frequently results in pre-exercise hyperglycemia, particularly if the exercise is performed 2 hours or more after the meal [2, 4, 5]. Even exercise in the fasting state in patients on continuous subcutaneous insulin infusion (CSII) promotes a drop in glycemia if basal insulin levels are not adjusted [5].

Post-exercise hypoglycemia is also very common in T1D, with roughly 50% of young patients developing the condition about 7-11 hours after the end of vigorous afternoon exercise [8]. Further, if insulin administration is used to correct post-exercise meal-related hyperglycemia (often called rebound hyperglycemia), severe post-exercise hypoglycemia may occur which may even result in death [9]. Patients can reduce the dose of meal time insulin administered with the dinner meal after late day exercise to reduce nocturnal hypoglycemia risk [10] or lower basal insulin delivery for 6 hours at bedtime [11] to help mitigate risk, but these strategies often result in hyperglycemia [10, 11]. Although extra carbohydrate ingestion not covered by insulin administration can help prevent hypoglycemia during and after exercise [12], excessive intake defeats the ability of the patient to have a negative caloric balance, thereby limiting the capacity for patients to control their body weight.

Patients on insulin pump therapy have the flexibility to reduce basal insulin delivery in anticipation of exercise and in recovery to help guard against hypoglycemia. The International Society for Pediatric and Adolescent Diabetes guidelines recommend that basal insulin reductions should be done 60-90 minutes before the start of exercise so that circulating insulin levels are lowered by the start of the activity [13]. This task is somewhat cumbersome and unpredictable and is usually not performed correctly, even by the most educated and motivated patients. Glucose production by the liver during moderate intensity exercise is primarily facilitated by a rise in the glucagon to insulin ratio [14] and patients with T1D have a reduction in this ratio during exercise because of a relative peripheral hyperinsulinemia [14] and impaired glucagon secretion [15], it may be better to attempt to change this ratio by the administration of glucagon at the onset of exercise [16]. The recent development of a more stable form of soluble glucagon (eg, Glucagon RTU from Xeris Pharmaceuticals, Inc. [Xeris]) has given researchers and clinicians the possibility of using this product as a preventative strategy to combat exercise-associated hypoglycemia.

4.2. Background

In Protocol No. XSMP-201, a Phase 2a clinical trial, Glucagon RTU was evaluated in a dose-seeking study among 12 adults aged 18 to 50 years with T1D. The study was conducted in an inpatient clinical research center setting, and tested doses of 75, 150, and 300 µg. Subjects were

studied on 3 separate occasions using 2 independent injections of glucagon on each study day. All treatments were well tolerated, no SAEs were observed and AEs were generally mild in nature and consisted primarily of pain or a burning sensation at the injection site. Observations of edema and erythema were generally mild and transient. Nausea occurred at the high dose only, in one- third of the patients.

Glucagon injections were made both after an overnight fast and several hours later, following an injection of insulin to mimic the amount they would have taken for a 30-g carbohydrate snack. The study results showed a clear dose response with an initial response observed after 15 to 20 minutes, and the peak time of response after 30 to 45 minutes, both after an overnight fast and following insulin to induce mild hypoglycemia. In all cases, subjects responded to the 150 and 300 µg doses with an increase of plasma glucose of 40 to 100 mg/dL following an overnight fast, and a somewhat smaller increase of 40 to 60 mg/dL following insulin. The 75 µg dose resulted in a smaller rise in glucose (+30 mg/dL) in most subjects, but in no case did the glucose continue to decrease after SC glucagon administration even at that lowest dose. On the basis of these results, a dose of 150 micrograms was selected for a follow-up study for prevention of exercise-induced hypoglycemia.

Protocol No. XSMP-203 was a single-blind, randomized 4-way crossover pilot study involving 15 adult subjects with T1D, ages 18 to 64 years, using continuous subcutaneous insulin infusion (CSII) and wearing a continuous glucose monitor. At 5 minutes prior to 45-minute sessions of moderate aerobic exercise, subjects received a 150-µg dose of Glucagon RTU or performed one of 3 alternate approaches for prevention of hypoglycemia: (1) consumed 20-gm glucose tablets, (2) implemented a 50% reduction in basal rate insulin, or (3) no intervention prior to exercise (ie, untreated control).

During exercise, plasma glucose increased slightly with Glucagon RTU compared to a decrease with control and insulin reduction, and a greater increase with glucose tablets. Insulin levels were not different among sessions, while glucagon increased with Glucagon RTU. Hypoglycemia (≤ 70 mg/dL (3.89 mmol/L)) was experienced by 6 subjects in the control arm, 5 subjects in the insulin reduction arm, and no subjects using glucose tablets or Glucagon RTU. A total of 5 subjects experienced hyperglycemia (≥ 250 mg/dL) with glucose tablets and 1 with Glucagon RTU.

There were no SAEs reported in the study and no subjects discontinued prematurely. No participant reported nausea during exercise, but 2 participants reported nausea with symptoms of bloating post-exercise after receiving Glucagon RTU.

4.3. Risk/Benefit Assessment

4.3.1. Known Potential Risks

One of the main complications of glycemic control with insulin is the emergence of hypoglycemia, and the absolute or relative excess of therapeutic insulin is the primary determinant of risk. Hypoglycemia in diabetes is defined as “all episodes of abnormally low plasma glucose concentration that expose the individual to potential harm” [5], and manifests clinically as diaphoresis, pallor, nausea, palpitations, tremor, anxiety, cognitive impairment, behavioral changes and psychomotor abnormalities, and loss of consciousness, seizure, and coma in severe

hypoglycemia. Recent reports have found that from 6 to 10% of deaths of patients with T1D are attributable to hypoglycemia [6]. The American Diabetes Association Workgroup recommends that patients with drug-treated diabetes (insulin secretagogues or insulin) become concerned about developing hypoglycemia at a plasma glucose concentration of ≤ 70 mg/dL (3.89 mmol/L) [17].

Therapy with insulin causes hypoglycemia during the course of established T1D and progressively more frequently over time in Type 2 diabetes. The U.K. Hypoglycemia Study Group reported an incidence of 110 hypoglycemic episodes per 100 patient-years in patients with T1D treated with insulin for <5 years, and an incidence of 320 episodes per 100 patient-years in those with T1D treated for >15 years [18]. People living with Type 1 diabetes suffer an average of two symptomatic hypoglycemic events per week – and a severe, temporarily disabling event approximately once a year [19]. Insulin-using people with Type 2 diabetes typically have several hypoglycemic episodes in a given year, 1-2 of these being severe episodes. There are currently approximately 1.4 million people with Type 1 diabetes and 3.8 million insulin-using people with Type 2 diabetes in the US alone [20]. On average, the total insulin-using patient population experiences about 3 million severe hypoglycemic events per year.

4.3.2. Known Potential Benefits

In response to the unmet medical need for a simple and ready-to-use glucagon for episodes of hypoglycemia, Xeris is developing a glucagon product. The Glucagon RTU (Glucagon Injection) utilizes Xeris' biocompatible, non-aqueous peptide/protein reformulation technology. This technology has allowed Xeris to create a concentrated, low volume, stable glucagon formulation, pre-mixed in a ready-to-use vial for administration by a single use syringe, and ultimately will allow development of a multi-dose pen. This creates a product with a number of advantages for the treatment of hypoglycemia:

- Ready-to-use treatment with no reconstitution required,
- Precise dosing to avoid overtreatment of low blood sugar,
- Rapid dosing due to room-temperature liquid stability, and
- Enhanced portability and availability in a multi-use format.

Current and future studies are aimed at evaluating the safety and efficacy of Glucagon RTU (Glucagon Injection) to provide patients with a better option for treatment and prevention of non-severe hypoglycemia.

5. OBJECTIVES AND ENDPOINTS

5.1. Objectives

5.1.1. Primary Objective

To evaluate whether the SC administration of Glucagon RTU (Glucagon Injection) just before exercise, with or without a 50% reduction in basal rate insulin, compared to a 50% basal rate insulin reduction alone, prevents the occurrence of hypoglycemia (ie, blood glucose \leq 70 mg/dL; 3.89 mmol/L) measured by blood glucose meter (BGM) during and after moderate-to-high intensity aerobic exercise by adult subjects with T1D in an outpatient setting.

5.1.2. Secondary Objectives

- To evaluate how Glucagon RTU (Glucagon Injection) contributes to prevention of hypoglycemia during exercise and post- exercise recovery
- To evaluate the effect of Glucagon RTU (Glucagon Injection) on insulin utilization during exercise.
- To evaluate the effect of Glucagon RTU (Glucagon Injection) on PROs BAPAD-1, HFS-II, and HCS after 12 weeks of outpatient exercise

5.1.3. Exploratory Objectives

- To evaluate the glycemic time in range associated with exercise sessions and post-exercise
- To evaluate the impact of Glucagon RTU (Glucagon Injection) on the quantity of glucose tabs used over time during exercise sessions
- To evaluate weight loss or weight maintenance over time
- To examine food intake both before and after exercise
- To examine the effects of exercise and Glucagon RTU on overnight hypoglycemia following episodes of exercise
- To evaluate the effects of exercise and Glucagon RTU use upon changes in hemoglobin A1c
- To evaluate the intensity and duration of the frequent exercise sessions
- To evaluate overall frequency of aerobic exercise over the study period

- To evaluate effects on exercise duration and intensity as well as daily activity metrics

5.2. Endpoints

5.2.1. Primary Endpoint

The primary endpoint is the incidence of hypoglycemia (ie., blood glucose \leq 70 mg/dL; 3.89 mmol/L) associated with an exercise session across 12 weeks of outpatient treatment as measured by a blood glucose meter (BGM).

5.2.2. Key Secondary Endpoints

- Glucose levels below target range, measured by unblinded CGM (inpatient and outpatient), defined as both time (in minutes) and mean decremental area over the curve (AUC(0-300 min) in minutes*mg/dL) during exercise:
 - • Below range, as defined by interstitial glucose (IG) \leq 70 mg/dL (\leq 3.89 mmol/L)
 - • Below range, as defined by IG between 54 to 70 mg/dL (3 – 3.89 mmol/L)
 - • Below range, as defined by IG $<$ 54 mg/dL ($<$ 3 mmol/L)
 - • Proportional time (percentage time within hypoglycemia IG \leq 70 mg/dL (3.89 mmol/L) and clinically significant hypoglycemia IG $<$ 54 mg/dL (3 3 mmol/L))
- Insulin utilization as reported by the subject at Baseline, Weeks 4, 8, and 12 in the Outpatient Phase.
- Change from Baseline to the end of the Outpatient Phase in PROs: Barriers to Physical Activity in Diabetes (Type 1) (BAPAD-1), Hypoglycemia Fear Survey (HFS-II), and Hypoglycemic Confidence Scale (HCS),

5.2.3. Other Secondary Endpoints

- Change from Baseline in insulin utilization as reported by the subject at Weeks 4, 8, and 12 in the Outpatient Phase.
- Exploratory EndpointsMean time and mean proportional time (%) within range, as defined by plasma glucose between 70 and 180 mg/dL (3.89 to 10 mmol/L) (CGM, 0 to 300 minutes with exercise)
- The time, proportional time (percentage), and mean incremental area under the curve (AUC) during which plasma glucose $>$ 180 mg/dL (10 mmol/L), and (AUC_(0- 300 min) in minutes*mg/dL) during exercise.

- The time, proportional time (percentage), and mean incremental area under the curve (AUC) during which plasma glucose >250 mg/dL (AUC(0- 5 hours) in minutes*mg/dL) during exercise.
- Incidence of overnight hypoglycemia as measured by CGM.
- Compare the glucose tablet utilization during exercise, across the 3 treatment arms.
- Compare food (carbohydrate) intake pre/post exercise across the 3 treatment arms.
- Compare the number of exercise sessions performed across the 3 treatment arms.
- Compare the number of minutes of exercise performed per week.
- Compare caloric expenditure during exercise, across 3 treatment arms.
- The change from Baseline in body weight will be measured and analyzed across the 3 treatment arms.
- Compare the number of steps taken and the distance achieved during exercise sessions across 3 treatments..
- The following assessments during exercise sessions will be captured from the wearable activity monitor: heart rate, daily steps, calories burned, distance covered, floors climbed, active minutes.
- Change from baseline in HbA1c

5.2.4. Safety Endpoints

Safety endpoints include the following: summaries of number of subjects (%) with adverse events, including serious adverse events; change from Baseline in vital signs and clinical laboratory test values; number of abnormal and clinically significant 12-lead ECG results. All safety parameter results will be listed.

6. STUDY DESIGN

6.1. Overall Design

This study is a randomized, placebo-controlled, double-blind, t2-treatment, 2-period, crossover comparison in a clinical research center (CRC) setting, followed by a randomized, placebo-controlled, double-blinded, 2-arm parallel comparison with a 3rd open-label arm in an outpatient setting to evaluate the preliminary efficacy and safety of Glucagon RTU to prevent exercise-induced hypoglycemia (EIH) in adults with Type 1 diabetes mellitus (T1D), who perform regular, moderate-to-high intensity aerobic exercise.

The CRC Stage will involve 2 daytime clinical research center (CRC, or comparable setting) exercise sessions 2 to 28 days apart, in a morning exercise session, for the following treatment assignments:

1. Insulin pump reduction (50% reduction in basal rate five minutes before exercise, for the duration of the exercise), and pre-exercise placebo injection (30 µL vehicle), or
2. Insulin pump reduction (50% reduction in basal rate five minutes before exercise, for the duration of the exercise), and pre-exercise Glucagon RTU (30 µL active - 0.15 mg).

At investigator discretion, the insulin pump rate can be reduced overnight based on the subject's medical history for the duration of the study.

BGM assessments (Yellow Springs Instrument [YSI] readings) during CRC visits will be at -15, 0, 30, 45, and 75 minutes from the start of exercise. Subjects will also wear unblinded CGM during both the CRC and Outpatient Stages of the study.

The Outpatient Stage will be 12 weeks in duration, during which subjects will be randomized to 1 of 3 parallel treatment arms, 2 of which are double-blinded, and 1 is open-label.

Subjects will receive:

1. Insulin pump reduction (50% reduction in basal rate five minutes before exercise, for the duration of the exercise), and pre-exercise placebo injection (30 µL vehicle), or
2. Insulin Pump reduction (50% reduction in basal rate five minutes before exercise, for the duration of the exercise), and pre-exercise Glucagon RTU (30 µL active - 0.15 mg), or
3. Pre-exercise Glucagon RTU (30 µL active - 0.15 mg) without pump changes.

Subjects will measure blood glucose using BGM at -15 and 0 minutes (ie, just before exercise) to establish a baseline, and after 30 minutes of exercise, 30 minutes post-exercise, and at the end of exercise (if greater than 30 minutes). Subjects will wear an unblinded CGM during the conduct of the study.

6.2. Justification for Dose

Mild to moderate hypoglycemia is common in individuals with T1D. Many individuals, particularly those under tight control, experience glucose levels ≤ 70 mg/dL (3.89 mmol/L) on a

daily or near-daily basis. When hypoglycemia is identified - either by measuring the glucose level or by symptoms, standard treatment consists of oral carbohydrate intake. This approach is generally successful in preventing more severe hypoglycemia and raising blood glucose concentrations. However, hyperglycemia often results and it can be difficult to quickly regain good control. In addition, the carbohydrate intake can make weight control challenging. Case reports have suggested that it may be more appealing to use small doses of glucagon to proactively raise the glucose level, avoiding the caloric value of the carbohydrate intake.

Although not labeled for use in situations other than severe hypoglycemia, small doses of glucagon have been shown to be particularly useful when an individual with T1D is unable to eat (e.g., young children who refuse or individuals with gastroenteritis or other illnesses). Haymond et al., reported that administration of glucagon by the subcutaneous route at a dose of 10 micrograms per year of age up to 150 micrograms was sufficient to increase the plasma glucose transiently (over 60 to 90 minutes) by 60 to 80 mg/dL and that repeated doses could be used for a subsequent mild hypoglycemic event without a worsening of nausea or vomiting [13]. This finding was confirmed in a report on the use of mini-dose glucagon in a pediatric practice in Australia, at a summer camp for children with diabetes, and in the inpatient setting [14, 15, 16]. While it is known that some individuals with T1D have successfully used mini-dose glucagon, little is known about frequency of use and response to treatment in an outpatient setting.

6.3. End of Study Definition

The end of the study is defined as the last visit date for the last subject in the study.

7. STUDY POPULATION

7.1. Inclusion Criteria

1. Clinical diagnosis of presumed autoimmune type 1 diabetes, receiving daily insulin via continuous subcutaneous insulin infusion.
2. Age 18 to < 65 years.
3. Duration of type 1 diabetes \geq 2 years.
4. Random C-peptide < 0.6 ng/mL (< 198 pmol/L).
5. Using insulin therapy by continuous subcutaneous insulin infusion pump for at least 6 months.
6. History of exercise-related hypoglycemia.
7. Performs aerobic exercise regularly (2-3 times per week), and desires to exercise per ADA guidelines (150 minutes per week). Examples of aerobic exercise include powerwalking, hiking, running/jogging, cycling, swimming, cross country skiing, and aerobic fitness classes.
8. Will abstain from the use of non-insulin diabetes therapies such as SGLT-2s, GLP-1s, and metformin for the duration of the study.
9. Subject must be willing to adhere to the protocol requirements for the duration of the study.
10. Subject has provided informed consent as evidenced by a signed/dated informed consent form completed before any trial-related activities occur.

7.2. Exclusion Criteria

1. Frequently experience hyperglycemia with exercise, in the clinical judgement of the investigator.
2. Pregnant and/ or Nursing: For female subjects of childbearing potential, there is a requirement for a negative urine pregnancy test and for agreement to use contraception and to refrain from breast feeding during the study, and for at least 1 week after the last dose of study drug. Acceptable contraception includes birth control pill / patch / vaginal ring, Depo-Provera, Norplant, an IUD, the double barrier method (the woman uses a diaphragm and spermicide and the man uses a condom), or abstinence. Note, there are no requirements for male subjects.
3. One or more severe hypoglycemic episodes in the past 12 months (as defined by an episode that required third party assistance for treatment).
4. Uses inhaled insulin.
5. HbA1c > 9.0% at Screening.
6. Renal insufficiency (serum creatinine greater than 3 mg/dL (0.17 mmol/L)).
7. Serum ALT or AST equal to or greater than 3 times the upper limit of normal.

Glucagon RTU (Glucagon Injection)
Protocol XSMP-204

Version 4.0

8. Hepatic synthetic insufficiency as defined as a serum albumin of less than 3 mg/dL (0.17 mmol/L); or serum bilirubin greater than 2 mg/dL (0.11 mmol/L).
9. Hematocrit of less than or equal to 30%.
10. Mean of triplicate BP readings at Screening where SBP <90 or >150 mm Hg, or DBP <50 or >100 mm Hg.
11. Clinically significant ECG abnormalities.
12. Use of > 2.0 U/kg total insulin dose per day.
13. Inadequate bilateral venous access in both arms.
14. Congestive heart failure, NYHA class III or IV.
15. Active malignancy within 5 years from Screening, except basal cell or squamous cell skin cancers.
16. Major surgical operation within 90 days prior to screening, or planned surgical operation during the study.
17. History of seizure disorders.
18. Current bleeding disorder, treatment with warfarin or any anticoagulants, or platelet count below 50,000.
19. History of pheochromocytoma or disorder with increased risk of pheochromocytoma (MEN 2, neurofibromatosis, or Von Hippel-Lindau disease).
20. History of insulinoma.
21. History of allergies to glucagon or glucagon-like products, or any history of significant hypersensitivity to glucagon or any related products or to any of the excipients(DMSO, mannitol, & trehalose) in the investigational formulation.
22. History of glycogen storage disease.
23. Subject tests positive for HIV, HCV or active HBV infection (HBsAg+) at Screening.
24. Any concurrent illness, other than diabetes, that is not controlled by a stable therapeutic regimen.
25. Active substance or alcohol abuse, in the opinion of the investigator. Subjects reporting active marijuana use or testing positive for THC via rapid urine test will be allowed to participate in the study at the discretion of the investigator.
26. Participation in other studies involving administration of an investigational therapeutic agent (drug or device) within 30 days or 5 half-lives, whichever is longer, before Screening for the current study and during participation in the current study.
27. Any reason the investigator deems exclusionary.

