8.7.1. Rescue Medicine

8.7.1.1. Oral Glucose Tablets

Standard of care for patients with symptoms of hypoglycemia and confirmed (BGM) blood glucose ≤ 70 mg/dL (3.89 mmol/L) is to take 16g (4 tabs, 4 g/tab) of glucose tabs, or per standard of care, and repeat the 16-g carbohydrate serving every 15 minutes until blood glucose is >70 mg/dL (3.89 mmol/L).

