10.1. Visit 1 – Screening (Day -28 to -3)

Prior to completing any screening activities, the investigator or study team member will obtain informed consent from each subject.

A Screening visit must be completed at least 3 days (to allow for receipt of blood test results), and no more than 28 days prior to the anticipated date of the first treatment visit (Day 1). The following evaluations will be completed during the screening visit:

1. Assessment of inclusion/exclusion criteria by a study investigator, including a review of the subject's medical history, and demographics.
2. Review of concomitant medications.
3. Physical exam, including measurement of height and weight (no shoes, lightly clothed), but excluding genital/pelvic exams.
4. 12-lead ECG after subject has completed a minimum 5-minute supine rest.
5. Vital signs measurements, including measurements of temperature, respiration rate, heart rate, and BP, after a 5-minute seated rest.
6. Urine pregnancy test for women of childbearing potential and discussion about study requirements regarding contraception.
7. Sample collection for urinary drug screen.
8. Collection of venous blood for complete blood count (without differential), serum chemistry, and screening for HIV, HBV, and HCV.
9. A fasting blood sample (minimum 8 hours) will be taken for measurement of plasma glucose, HbA1c, and C-peptide.
10. Assessment of baseline AEs.

Once laboratory results are obtained and a final determination of eligibility is made, subjects will be contacted to schedule the CGM Placement Visit.

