10.3. CRC Phase

10.3.1. Visit 3 – Treatment 1 (Day 1) / Visit 4 Treatment 2 (Day 3-29) Clinic Arrival

1. Subjects will arrive to clinic in the morning, after an overnight fast of at least 8 hours.
 - Subjects may proceed with exercise if BG is 100-180 mg/dL (5.56 – 10 mmol/L), as measured by the blood glucose meter.
 - If the subject's blood glucose is below 100 mg/dL the subject is allowed to take dextrose tabs (e.g., 2-4 tabs) per discretion, to bring the subject into the required blood glucose range. Before initiating study treatment, at least 30 minutes should have passed from the last dose of administered dextrose tabs and the subject's glucose level should be within the range of 100 to 180 mg/dL
 - Prior to beginning the exercise session, if the blood glucose is >180 mg/dL after repeat test, then the investigator may treat with an intravenous (IV) bolus dose of regular insulin, per discretion, to bring the subject into the required blood glucose range. Before initiating study treatment, at least 40 minutes should have passed from the last dose of administered insulin and the subject's glucose level should be within the range of 100 to 180 mg/dL
 - If the subject's blood glucose cannot be optimized to 80 to 150 mg/dL within 2 hours, then the visit should be rescheduled after a minimum 24 hour wait, per investigator's discretion.
 - At discretion, the investigator may reschedule the visit to occur after a minimum wait of 24 hours. The visit should be re-scheduled so it occurs within the originally defined visit window. For example, a rescheduled Visit 3 (CRC 1) should occur within 28 days of Visit 1 (Screening), while a rescheduled Visit 4 (CRC 2) should occur within 28 days of a completed Visit 3 (CRC 1).
2. It will be confirmed that the CGM placed at Visit 2 is active and that the subject has followed calibration instructions.
3. Concomitant medications will be assessed.
4. Vital signs measurements, including measurements of temperature, respiration rate, heart rate, and BP, after a 5-minute seated rest.
5. Urine pregnancy test for women of childbearing potential.

6. Blood sample for immunogenicity testing (Only performed at Visit 3).
7. The wearable activity monitor will be worn by the subject during each exercise session.
 - Subject will wear both the Fitbit® Ionic and Polar Beat H10 heart rate sensor provided by the site during these visits.

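### Exclusion criteria 6 and 8 convert creatinine, albumin and bilirubin to mmol/L with the glucose factor of 18, so each limit carries two unequal cut-offs and no text says which governs

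*Protocol*

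**What the plan says.** Protocol section 7.2 gives three laboratory limits in two units each:

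- Criterion 6: "Renal insufficiency (serum creatinine greater than 3 mg/dL (0.17 mmol/L".
- Criterion 8, two limits joined by an or: "serum albumin of less than 3 mg/dL (0.17 mmol/L); or serum bilirubin greater than 2 mg/dL (0.11 mmol/L".

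Elsewhere the protocol prints paired units for glucose, for example "until blood glucose is >70 mg/dL (3.89 mmol/L" in section 8.7.1.1 and "Subjects may proceed with exercise if BG is 100-180 mg/dL (5.56 – 10 mmol/L), as measured by the blood glucose meter" in section 10.3.1. For C-peptide, inclusion criterion 4 in section 7.1 reads "Random C-peptide < 0.6 ng/mL (< 198 pmol/L".

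These limits are applied at screening. Section 10.1 schedules the next visit "Once laboratory results are obtained and a final determination of eligibility is made". The SAP gives no laboratory limits of its own, and its section 4.4 records no changes from the protocol.

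**The concern.** Creatinine and albumin, at the same mg/dL value, are given the same mmol/L value. A conversion between mass and molar units depends on the molar mass of the substance, so identical conversions for a small metabolite and a large protein cannot both be right. The figures look as if the glucose conversion was applied to all three analytes.

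If so, each criterion contains two thresholds that are not equivalent. A single result could make a subject eligible under one printed figure and excluded under the other, depending on the unit in which the laboratory reports. These are renal and hepatic safety exclusions, and each should have one meaning.

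**Working it through.** **Step 1. The protocol's glucose ratio (mg/dL divided by mmol/L).**

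- 70 / 3.89 = 17.99 (section 8.7.1.1)
- 100 / 5.56 = 17.99 and 180 / 10 = 18.0 (section 10.3.1)
- 54 / 3 = 18.0 (section 9.3.1.1)

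**Step 2. Reproduce the printed limits by dividing by 18.**

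- Creatinine and albumin: 3 / 18 = 0.1667, which rounds to the printed 0.17.
- Bilirubin: 2 / 18 = 0.1111, which rounds to the printed 0.11.

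All three reproduce exactly.

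**Step 3. Molar mass implied by each printed pair** (g/mol = 10 × mg/dL ÷ mmol/L). The range allows for rounding of the mmol/L figure to two decimals.

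| Analyte | Calculation | Implied g/mol | Rounding range |
|---|---|---|---|
| Glucose | 700 / 3.89 | 179.9 | not needed |
| Creatinine | 30 / 0.17 | 176.5 | 171.4–181.8 |
| Albumin | 30 / 0.17 | 176.5 | 171.4–181.8 |
| Bilirubin | 20 / 0.11 | 181.8 | 173.9–190.5 |

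The last three ranges all contain 180, the glucose value. By contrast, the C-peptide pair gives 0.6 × 10⁻⁶ g/L ÷ 198 × 10⁻¹² mol/L = 3,030 g/mol, so the protocol does use a factor specific to the analyte there.

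Steps 1 to 3 use printed figures only.

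**Step 4. Size of each disagreement.** This needs molar masses, which the documents do not give. Assumed: creatinine 113.12, bilirubin 584.66, albumin 66,500 g/mol (range 65,000–69,000). Formulas: mmol/L = 10 × mg/dL ÷ molar mass; mg/dL = mmol/L × molar mass ÷ 10.

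- **Creatinine.** 3 mg/dL = 30 / 113.12 = 0.265 mmol/L, against 0.17 printed. Conversely, 0.17 × 113.12 / 10 = 1.92 mg/dL (1.87–1.98 allowing for rounding). Fold difference 3 / 1.92 = 1.56. Results from about 1.9 to 3 mg/dL are excluded by the molar figure and eligible by the mass figure.
- **Bilirubin.** 2 mg/dL = 20 / 584.66 = 0.034 mmol/L, against 0.11 printed. Conversely, 0.11 × 584.66 / 10 = 6.43 mg/dL (6.1–6.7). Fold difference 6.43 / 2 = 3.22. Results from about 2 to 6.4 mg/dL are eligible by the molar figure and excluded by the mass figure.
- **Albumin.** 3 mg/dL = 30 / 66,500 = 0.00045 mmol/L, against 0.17 printed. Conversely, 0.17 × 66,500 / 10 = 1,130.5 mg/dL, or 1.13 g/dL. Fold difference 1,130.5 / 3 = 377 (368 at 65,000; 391 at 69,000). If g/dL was meant in place of mg/dL, the pair still disagrees: 3 / 1.13 = 2.65-fold (2.56–2.71).

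**The case against.** The best reply is that the layout shows which unit governs. The protocol puts the mass unit first and the molar value in parentheses, for glucose and C-peptide alike, so criteria 6 and 8 read naturally as mg/dL limits with a bad conversion attached. That reading is reasonable, but no sentence states it. The protocol's own history also weakens it: the summary of changes from version 2.0 to 3.0 explains that the pmol/L value for C-peptide was added because the local laboratory reports in that unit. A parenthetical figure can therefore be the one the site applies. This does not show how creatinine, albumin or bilirubin are reported, and the documents do not say.

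Three further points stand at least in part:

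- **Albumin.** If ordinary serum albumin is several g/dL (an assumption), neither 3 mg/dL nor about 1.13 g/dL would exclude more than a rare subject. The 377-fold gap then has little practical meaning, and the problem is more likely a wrong mass unit. The working conflicts are creatinine and bilirubin.
- **Reach.** The population is adults who exercise regularly, so few may fall in the disputed bands. Criteria 7 (transaminases), 24 (uncontrolled illness) and 27 (investigator's judgement) can catch some of them. They can only add exclusions, however, and cannot readmit someone excluded by the stricter creatinine figure. The or in criterion 8 leaves bilirubin able to exclude a subject when the albumin part does not, but an inert albumin part is no backstop for bilirubin.
- **Analysis.** The ITT and Safety populations do not depend on these limits. Per Protocol membership depends on key exclusion criteria, which protocol section 12.3 leaves to the SAP and SAP section 4.1 does not list, so any effect there is unknown.

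**Conclusion.** The concern holds. That one factor of 18 was applied to three substances other than glucose follows from the printed figures alone, and nothing in either document corrects the pairs or names the governing unit.

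The size rests on the assumed molar masses: about 1.6-fold for creatinine and 3.2-fold for bilirubin, in opposite directions for strictness, so reading everything in one unit system does not err consistently on the cautious side. The albumin disagreement is large on paper and probably immaterial to eligibility decisions, but its unit still needs attention.

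This is an ambiguity in safety eligibility limits that should be corrected. It is not evidence that any subject was wrongly enrolled or excluded, and the sample size and primary test are untouched.

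**What to change.** For each of the three limits in criteria 6 and 8, the sponsor should state which figure is intended, print the other as its correct arithmetic equivalent, and say which unit governs. The mass unit for albumin should be reconciled at the same time. No threshold is proposed here; the choice is the sponsor's.

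Existing screening creatinine, albumin and bilirubin results should then be compared with the reconciled limits, and any subject whose eligibility changes should be documented.

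The cost is a short protocol clarification and a check of data already collected. No new tests are needed.
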